4.1.8 Drug accountability

The investigator or designee will receive the investigational drugs delivered by a clinical research organisation (CRO) appointed by the sponsor when the following requirements are fulfilled:

- Approval of the clinical trial protocol by the institutional review board (IRB) / ethics committee (EC),
- Availability of a signed and dated clinical trial contract between the sponsor and the head of the investigational site,
- Approval/notification of the regulatory authority, e.g. competent authority,
- Availability of the curriculum vitae of the Principal Investigator,
- Availability of a signed and dated clinical trial protocol,
- In countries where it is required, availability of the proof of a medical license for the Principal Investigator,
- In the US, availability of FDA Form 1572.

Investigational drugs are not allowed to be used outside the context of this protocol. They must not be forwarded to other investigators or clinics. Patients should be instructed to return unused investigational drug.

The investigator or designee must maintain records of the product's delivery to the trial site, the inventory at the site, the use by each patient, and the return to the sponsor or warehouse / drug distribution centre or alternative disposal of unused products. If applicable, the sponsor or warehouse / drug distribution centre will maintain records of the disposal.

These records will include dates, quantities, batch / serial numbers, expiry ('use- by') dates, and the unique code numbers assigned to the investigational medicinal product and trial patients. The investigator or designee will maintain records that document adequately that the patients were provided the doses specified by the Clinical Trial Protocol (CTP) and reconcile all investigational medicinal products received from the sponsor. At the time of return to the sponsor or appointed CRO, the investigator or designee must verify that all unused or partially used drug supplies have been returned by the clinical trial patient and that no remaining supplies are in the investigator's possession.

4.2 OTHER TREATMENTS, EMERGENCY PROCEDURES, RESTRICTIONS

4.2.1 Other treatments and emergency procedures

Rescue medications to reverse the action of nintedanib are not available.

There are no special emergency procedures to be followed.

Dose reduction (from 150 mg bid to 100 mg bid) or treatment interruption should be considered to manage adverse events. No further dose reduction is possible for patients on the 100 mg bid dose. In case of persistent adverse events observed at this dose, or severe effects at 150 mg bid, permanent treatment discontinuation should be considered.

Dose reduction from 150 mg bid to 100 mg bid was possible at Visit 1 if required to manage adverse events identified at the end of the INBUILD® trial.

Treatment interruption and reduction and re-escalation are repeatedly possible.

Table 4.2.1: 1 Allowed treatment reduction / interruption periods

	AEs considered drug related	AEs or other events not considered drug related
Maximum interruption	4 weeks	12 weeks
Recommended restart	with reduced dose (100 mg bid)	with the same dose (100 mg bid or 150 mg bid)
Re-escalation	Any time to 150 mg bid	----

4.2.1.1 Management of diarrhoea

Diarrhoea is a known side effect of nintedanib treatment (see section [1.2](#)). However, potential causes for diarrhoea other than study medication should always be considered and treated accordingly (e.g. viral infections, bacterial overgrowth, antibiotic treatment).

Diarrhoea should be managed as early as possible after onset of first symptoms with standard antidiarrhoeal symptomatic treatment, e.g. loperamide.

If diarrhoea persists despite optimal symptomatic treatment, treatment interruption and dose reduction of nintedanib should be considered based on the recommendations described in table 4.2.1.1:1.

Table 4.2.1.1: 1 Management of diarrhoea (considered related to trial medication)

Description	Symptomatic Treatment*	Action with trial medication
Diarrhoea with increase of <4 stools per day over baseline ¹ .	Initiate anti-diarrhoeal medicines at first signs of symptoms (e.g. 4 mg loperamide followed by 2 mg after each loose stool or every 2-4 hours to a maximum of 16 mg/day) until bowel movements cease for 12 hours.	Continue same trial medication dose.
Diarrhoea with increase of 4 to 6 stools per day over baseline ¹ .	Initiate/continue anti-diarrhoeal medicines; If diarrhoea of this severity persists for ≥48 to 72 hours assess for dehydration and electrolyte imbalance; In addition, consider IV fluids and electrolyte replacement as clinically indicated.	If diarrhoea persists for ≥48 to 72 hours despite optimal symptomatic care: 1. Interrupt trial medication until recovery. 2. Reduce dose to 100 mg bid after recovery. 3. Re-escalate to 150 mg bid within 4 weeks if deemed clinically appropriate.
Diarrhoea with increase of ≥7 stools per day over baseline ¹ ; stool incontinence, or life threatening consequences.	Follow recommendations above. In addition, consider stool work-up to exclude infectious colitis; adequate IV fluid replacement ≥24 hours, hospitalisation as clinically indicated; consider referral to a GI specialist to rule out potential differential diagnoses.	1. Interrupt trial medication until recovery. 2. Reduce dose to 100 mg bid after recovery. 3. Consider re-escalation within 4 weeks to 150 mg bid if deemed clinically appropriate. In case of reoccurrence of diarrhoea of this severity despite optimal symptomatic treatment and dose reduction, treatment with trial medication should be permanently discontinued.

Footnotes:

* Other causes for diarrhoea should always be considered and treated accordingly (e.g. viral infections, bacterial overgrowth, antibiotic treatment)

¹ Baseline defined as usual stools/day prior to visit 1.

4.2.1.2 Management of liver enzyme elevation

Evaluate the concomitant use of other drugs known to cause liver enzyme elevations. For a detailed guidance on how to manage liver enzyme elevations, please refer to Table 4.2.1.2: 1.

Table 4.2.1.2: 1 Management of liver enzyme elevations

AST or ALT increase to			Signs of hepatic injury* (section 5.2.5.1.4)	
>1.5x to <3x ULN	$\geq 3x$ to <5x ULN and no signs of hepatic injury (section 5.2.5.1.4)	$\geq 5x$ to <8x ULN and no signs of hepatic injury (section 5.2.5.1.4)		
Continue as planned ¹	Reduce dose or interrupt trial medication ²	Interrupt trial medication	Permanently discontinue / interrupt trial medication	
	Close observation ³ After 2 weeks or any time later	Close observation ³ After 2 weeks or any time later		CLINICAL EVALUATION OF HEPATIC-INJURY⁴ (section 5.2.5.1.4)
<3x ULN	$\geq 3x$ ULN	< 3x ULN	$\geq 3x$ ULN	
Reduced: return to initial dose. Interrupted: restart at reduced dose. Monitor every 2 weeks for at least 8 weeks	Permanently discontinue trial medication Close observation ³	Restart at reduced dose Monitor weekly for 4 weeks, then every 2 weeks for at least 8 weeks	Permanently discontinue trial medication. Close observation ³	

Footnotes:

*Signs of hepatic injury are defined as

- ALT and/or AST ≥ 8 fold ULN
- ALT and/or AST ≥ 3 fold ULN and total bilirubin ≥ 2 fold ULN
- ALT and/or AST ≥ 3 fold ULN and unexplained INR $> 1,5$
- ALT and/or AST ≥ 3 fold ULN and unexplained eosinophilia ($> 5\%$)
- ALT and/or AST ≥ 3 fold ULN and appearance of fatigue, nausea, vomiting, right upper abdominal quadrant pain or tenderness, fever and/or rash

¹ According to visit schedule. Consider additional control visits as adequate.

² To be decided by Investigator, based on individual risk assessment.

³ Close observation: Re-test ALT and AST, alkaline phosphatase, total bilirubin, and eosinophils within 48 to 72 hours, then after approximately 7 days and after approximately 2 weeks by using intermediate visit lab kit.

⁴ If clear evidence for alternative cause for hepatic injury was identified and resolved (i.e. relation to trial medication excluded, hepatic injury confirmed to have alternative explanation [other than use of IMP]): return to trial medication would be possible, after consultation with the sponsor. Prior to restart, liver laboratory values must be normal. Monitor weekly for first 4 weeks of re-introduction and every 2 weeks for the following 8 weeks.

Initial assessment and blood sampling for liver enzyme elevation follow up should be performed at the investigational site. Blood samples for additional monitoring may be collected at the investigational site, primary care physician or external laboratory with specific trial lab kits and sent to the central laboratory for analysis.

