Administration of nintedanib was associated with elevations of liver enzymes (ALT, AST, ALK, GGT). Administration of nintedanib was also associated with elevations of bilirubin. The dosing regimen, that includes dose reduction and dosing interruptions, was effective in the management of liver enzyme and bilirubin elevations (see section [4.2.1](#)). Cases of drug-induced liver injury (DILI) have been observed with nintedanib treatment. In the post-marketing period, non-serious and serious cases of drug-induced liver injury, including severe liver injury with fatal outcome, have been reported. The majority of hepatic events occur within the first three months of treatment.

Based on data from clinical trials and post-marketing and supported by population pharmacokinetic models, patients with low body weight (<65 kg), Asian and female patients have a higher risk of liver enzyme elevations with nintedanib treatment.

Patients at known risk for bleeding or who required fibrinolysis, full-dose therapeutic anticoagulation, or high dose antiplatelet therapy were excluded from participation in the

nintedanib in IPF trials, and initiation of any of these therapies during the course of the trials required discontinuation of the study medication. In the IPF phase III trials, bleeding events were slightly more frequently reported in patients treated with nintedanib than in those receiving placebo. In the post-marketing period non-serious and serious bleeding events, some of which were fatal, have been observed. Considering that VEGFR inhibition might potentially be associated with an increased risk of bleeding, patients with full-dose anticoagulation should only be treated with nintedanib if the anticipated benefit outweighs the potential risk.

Thromboembolic events were more frequently reported in the nintedanib group than in the placebo group. This difference was due to arterial thromboembolic events, specifically due to myocardial infarction. The proportion of patients with cardiac adverse events and cardiac SAEs, and especially AEs reflecting ischaemic heart disease, was balanced between the nintedanib and placebo groups. Based on the available clinical data, and considering the mechanism of action of nintedanib, no definitive conclusion on the risk of thromboembolic events can be drawn. Arterial thromboembolism is considered an important potential risk of nintedanib treatment in IPF.

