5.2.3 Safety laboratory parameters

Safety laboratory parameters to be assessed are listed in Table [5.2.3:1](#). For the sampling time points please see the Flowchart.

All analyses will be performed by a central laboratory, the respective reference ranges will be provided in the ISF.

Patients do not have to be fasted for the blood sampling for the safety laboratory. Venous whole blood will be collected in appropriate syringes provided by the sponsor through the assigned central laboratory. Details regarding centrifuge, processing, storage and shipment of samples will be determined by the central laboratory in accordance with the sponsor. The Investigators will be informed and instructed by the central lab and detailed documentation (Laboratory Manual) will be included in the ISF.

The central laboratory will send reports to the investigator. It is the responsibility of the investigator to evaluate the laboratory reports. Clinically relevant abnormal findings as judged by the investigator will be reported as adverse events (please refer to section [5.2.5.2](#)).

In case the criteria for hepatic injury are fulfilled, a number of additional measures will be performed (please see section [5.2.5.1.4](#) and the DILI Checklist provided in the ISF). The amount of blood taken from the patient concerned will be increased due to this additional sampling.

The central laboratory will transfer the results of the analysis to the sponsor.

The laboratory tests at regular site visits (Visit 1, Visit 3, Visit 5, Visit 6, Visit 7, Visit 8 to X) will include:

Table 5.2.3: 1 Laboratory tests

Category	Laboratory test
Haematology	Red blood cell count (RBC) Haemoglobin (Hb) Haematocrit (Hct) Mean corpuscular volume White blood cell count including differential Platelet count
Biochemistry	Aspartate aminotransferase (AST) Alanine transaminase (ALT) Gamma-glutamyl transferase (GGT) Alkaline phosphatase (ALK) Creatine kinase (CK) Lactate dehydrogenase (LDH) Total protein Total bilirubin Creatinine Glucose (non fasting) Uric acid Thyroid stimulating hormone (at V1 then every 48 weeks and at EOT)
Electrolytes	Sodium Potassium Calcium Chloride Inorganic phosphorus
Coagulation	International normalised ratio (INR) Partial thromboplastin time (PTT) Prothrombin time (PT)
Local Urine dipstick pregnancy test in all women of childbearing potential. If urine test is not acceptable to local authorities, a blood test must be done at a local laboratory.	

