The laboratory tests at Visit 2, Visit 4, Visit 5a, Visit 6a and Visit 7a will include:

Table 5.2.3: 2

Laboratory tests at Visit 2, Visit 4, Visit 5a, Visit 6a and Visit 7a

Category	Laboratory test
Biochemistry	Total protein, creatinine, electrolytes (sodium, potassium, calcium, chloride, inorganic phosphorus) and liver function (AST, ALT, GGT, alkaline phosphatase, and total bilirubin)
Local Urine dipstick pregnancy test in all women of childbearing potential. If urine test is not acceptable to local authorities, a blood test must be done at a local laboratory.	

The laboratory samples taken at intermediate ‘a’ visits (Visits 5a, 6a and 7a) and any samples taken for additional safety monitoring (see section [4.2.1.2](#)) may be collected at the office of a local doctor using trial specific lab kits that will be sent to a central laboratory for analyses. These kits will be provided to patients at study visits as applicable.

Creatinine clearance will be calculated based on serum creatinine according to Cockcroft and Gault ([R96-0690](#)), Appendix [10.2](#)).

If laboratory values indicate abnormality, adequate and more frequent blood sampling may be performed at the discretion of the Investigator. Dependent on concomitant treatments, additional safety monitoring should be considered at the discretion of the investigator.

In case of liver function value elevations, close monitoring must be ensured by the Investigator. Refer to section [4.2.1.2](#) for monitoring elevations and section [3.3.4](#) for withdrawal criteria.

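### Two of the five hepatic-injury stop criteria cannot be evaluated on the panel listed for Visits 2 and 4, and the prescribed re-tests never add INR

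*Protocol*

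**What the plan says.** Protocol 5.2.5.1.4 defines five signs of hepatic injury: ALT/AST of at least 8xULN, or ALT/AST of at least 3xULN together with raised bilirubin, unexplained INR above 1.5, unexplained eosinophilia above 5%, or listed symptoms. The bilirubin, INR and eosinophil results must come from the same sample as the transaminase elevation. Any sign requires an immediate stop, and hepatic injury is one of the two AESIs.

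The dosing table in Protocol 4.2.1.2 limits its columns for 3 to <5xULN and 5 to <8xULN to patients with the stated elevation "and no signs of hepatic injury (section 5.2.5.1.4". Footnote 3 defines close observation: "Re-test ALT and AST, alkaline phosphatase, total bilirubin, and eosinophils within 48 to 72 hours", again at about 7 days, and "after approximately 2 weeks by using intermediate visit lab kit". INR is not named. Protocol 4.2.2.2 also pairs eosinophils with the intermediate kit.

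Protocol 5.2.3 has two panels. The full one, with differential and INR, applies to "The laboratory tests at regular site visits (Visit 1, Visit 3, Visit 5, Visit 6, Visit 7, Visit 8 to X"). The reduced one, Table 5.2.3:2, applies to Visits 2, 4, 5a, 6a and 7a and lists "Total protein, creatinine, electrolytes (sodium, potassium, calcium, chloride, inorganic phosphorus) and liver function (AST, ALT, GGT, alkaline phosphatase, and total bilirubin"), plus a pregnancy test. Protocol 6.2.2 and the Flowchart make only the 'a' visits optional; Visits 2 and 4 are scheduled for everyone.

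SAP 5.4.4 uses the same five signs with the same-sample condition. It shows no rule for a sample in which the analyte was not measured.

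**The concern.** There are two separate points.

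- **Eosinophils: a mismatch.** Two sections order them on the intermediate kit, but the table listing the tests at the intermediate visits does not include them.
- **INR: a gap.** It is missing from both the reduced panel and all three re-tests. After an elevation at Visit 2 or 4 it is measured only at the next full panel or if the investigator chooses to order it. It then counts only if ALT/AST is still at least 3xULN in that later draw.

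The dosing columns therefore require the absence of signs that the listed tests cannot rule out. The timing adds weight. Protocol 1.2 states: "The majority of hepatic events occur within the first three months of treatment". Protocol 3.3 says former placebo patients first receive nintedanib at Visit 1.

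Consider a patient at 3 to <5xULN at Visit 2 or 4 whose only sign would be INR above 1.5. If the sign is seen, the drug stops, and footnote 4 allows a restart only with a resolved alternative cause, sponsor consultation and normal liver values. If it is not seen, the patient may stay on a reduced dose and, once below 3xULN, follow "Reduced: return to initial dose. Interrupted: restart at reduced dose".

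On the reporting side, the SAP's hepatic-injury proportion and protocol deviation C2a (SAP 6.2) use the same signs, so they could miss the same cases.

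**Working it through.** The documents give no figure to reproduce. The check matches the criteria against the panels, then counts draws and days.

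**Step 1. Criteria against Table 5.2.3:2**

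| Sign (Protocol 5.2.5.1.4) | Needs | Evaluable on the reduced panel? |
|---|---|---|
| ALT/AST ≥8xULN | ALT, AST | Yes |
| ≥3xULN + bilirubin ≥2xULN | bilirubin, same draw | Yes |
| ≥3xULN + INR >1.5 | INR, same draw | No |
| ≥3xULN + eosinophils >5% | differential, same draw | No |
| ≥3xULN + symptoms | clinical assessment | Yes |

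Two of five cannot be evaluated.

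**Step 2. Share of mandatory post-baseline draws with the reduced panel** (Flowchart and Protocol 6.2.2; Visit 1 is the baseline draw, 'a' visits are excluded as optional)

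- To Week 12: Visits 2, 3, 4, 5. 2/4 = 50%.
- To Week 48: add Visits 6, 7, 8. 2/7 = 28.6%.
- To Week 96: add Visits 9 to 12. 2/11 = 18.2%.

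These are shares of scheduled draws, not rates of missed cases.

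**Step 3. When the next scheduled INR arrives** (visit windows ±3 days)

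- *After Visit 2 (Day 15).* Re-tests fall on Days 17–18, about 22 and about 29. Visit 3, with the full panel, is planned for Day 29. With windows, Visit 2 + 14 is Days 26–32 and Visit 3 is Days 26–32, so they differ by −6 to +6 days.
- *After Visit 4 (Day 57).* Re-tests fall on Days 59–60, about 64 and about 71. Visit 5 is planned for Day 85. Planned gap: 85 − 71 = 14 days. With windows, Visit 4 + 14 is Days 68–74 and Visit 5 is Days 82–88. The gap runs from 82 − 74 = 8 to 88 − 68 = 20 days.

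So the two-week dosing decision after Visit 4 is reached with no scheduled INR. Footnote 3 itself orders INR at 0 of 3 re-tests.

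**Step 4. Does another provision supply the INR?**

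- The DILI checklist (Protocol 5.2.3, 5.2.5.1.4) starts once the criteria are met, so it cannot supply the result needed to meet them.
- The unscheduled test for clinical symptoms (Protocol 5.2.5.1.4) names ALT, AST and total bilirubin only.
- Protocol 5.2.3 says "adequate and more frequent blood sampling may be performed at the discretion of the Investigator", which permits an INR but does not require one.

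**Step 5. After the change.** With a differential and INR at Visits 2 and 4, all five signs can be evaluated at 4 of 4 draws to Week 12, against 2 of 4 now.

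**The case against.** The strongest reply has five parts.

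1. **Kit contents are not visible.** Table 5.2.3:2 lists tests by visit and is not a kit inventory. Two sections say the kit covers eosinophils, so it probably does, and the first re-test would then supply them within 48 to 72 hours while ALT/AST stays at least 3xULN. This stands: for eosinophils, what remains is the omission at the first elevated draw and a text that needs aligning.
2. **Visit 3 covers Visit 2.** A full panel is planned for the day of the two-week re-test. This stands for scheduling. However, a Day 29 INR counts only if ALT/AST is still at least 3xULN, and the table then already requires permanent discontinuation. On the planned days it comes too late to change the preceding two weeks of dosing.
3. **The chain to harm is long.** It needs 3 to <5xULN, unexplained INR above 1.5, bilirubin below 2xULN, none of the listed symptoms, and a choice to reduce rather than interrupt. Nausea alone was reported in 28.9% of nintedanib patients in the parent trial, so the symptom sign is broad. At 5xULN or more the drug is interrupted at once. Values still at least 3xULN after two weeks mean permanent discontinuation, and patients who resume are monitored every two weeks for at least eight weeks. All of this stands and limits the severity.
4. **The early-risk argument applies mainly to former placebo patients.** Former nintedanib patients already had at least 52 weeks of treatment. This also stands.
5. **No SAP error is shown.** SAP 7 provides a missing category, and laboratory handling follows a company standard outside the documents. This is right: the handling is unknown.

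None of these supplies an INR at Visits 2 and 4 or at the early re-tests.

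**Conclusion.** The concern holds and should be fixed. As listed, 2 of 5 hepatic-injury signs cannot be evaluated at 2 of 4 mandatory post-baseline draws to Week 12. INR is ordered at none of the three re-tests, and after Visit 4 the next scheduled INR comes 14 days (8 to 20) after the two-week decision. The counts follow directly from the protocol.

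The consequence is less certain. It depends on the kit contents, laboratory manual and DILI checklist, none of which is visible, and the documents give no frequency for INR-only or eosinophil-only cases. The INR gap is firmer than the eosinophil mismatch, which may be only a matter of wording. The plausible effect is about two weeks on a reduced dose instead of a stop, followed by an easier return to treatment, in an unknown number of patients. The incidence of overall adverse events is essentially unaffected.

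**What to change.** - **Table 5.2.3:2:** add white cell count with differential, so the table and kit agree with footnote 3 and Protocol 4.2.2.2.
- **Footnote 3:** add INR to the re-tests. The 48-to-72-hour sample matters most, because it comes before the two-week decision.
- **Visits 2 and 4:** add INR to the site draws. It is not essential at the optional off-site 'a' visits.
- **SAP 5.4.4:** keep the same-sample definition, and report how many draws and subjects with ALT/AST of at least 3xULN had no same-draw INR or eosinophil result.

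**Cost.** One or two extra tubes in existing draws. With about 480 patients and no dropout, this is at most 480 × 2 = 960 INR tests at Visits 2 and 4, plus up to 3 per elevation episode. For differentials it is about 480 × 2 = 960, or 480 × 5 = 2,400 if every 'a' visit is done. Protocol 4.2.1.2 already places the initial follow-up sample at the site; later re-tests may be off site, where a coagulation tube adds handling and shipment. The document changes are a table edit, a footnote edit and one SAP count. The downside is a few more flagged cases.

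Protocol 1.4 already describes the start of recruitment in the past tense, so the Visit 2 and 4 change may come too late for many patients. The footnote 3 change applies throughout treatment.
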